8. GENERAL ISSUES FOR STATISTICAL ANALYSIS

8.1 General Statistical Methodology

Descriptive summaries will be provided where appropriate for each of the primary and secondary variables. Tables in the ITT population will summarize data by randomized treatment, tables in the PP and Safety populations will summarize data by treatment actually received if not otherwise specified.

Primary and secondary effectiveness analysis will be conducted in the ITT and the PP populations. All safety data analyses will be performed in the Safety Population.

Health economic and QoL tables will be completed for the ITT population unless otherwise specified. According to the protocol it was planned to use the PP population for health economic and QoL tables, but this was changed to ITT population to perform the analysis based on the randomized treatment groups.

Continuous, quantitative, variable summaries will include the number of subjects (N) with non-missing values, mean, standard deviation (SD), median, minimum, maximum, and quartiles, unless otherwise specified.

Categorical, qualitative, variable summaries will include the frequency and percentage (where applicable) of subjects who are in the particular category. In general, the denominator for the percentage calculation will be based upon the total number of subjects in the study population for the treatment groups unless otherwise specified.

The baseline value will be defined as value entered to the screening/baseline page of the eCRF (terminology screening/baseline is not used consistently in eCRF, but there is only one screening/baseline assessment planned according to protocol).

All analyses will be performed using SAS[®] Software version 9.1.3 or later. ADDPLAN[®] version 5.0.2 or later and East version 5.3 or later may also be used.

For re-calculating of operating characteristics for the analyses of the primary endpoint, the software WinLD will be used.

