5. The recognized reasons for patients not doing well on drug therapy are as follows:
  - a. Patients failing to take the medication as prescribed – called “non-adherence”:
    - i. Missed days (drug holidays) – recurring disease symptoms or sudden drug-related side effects, if drug rebound effect, after resuming medication.
    - ii. Irregular timing, resulting in low concentrations of active drug at some points or too high concentrations of active drug when medication is taken at close intervals (may manifest as side effect problem).
    - iii. Medication dropout – patient takes no drug but does not share this information with his/her physician – unexpected disease progression.
  - b. Patient cannot tolerate medication, even if compliant with prescribed regimen (side effects):
    - i. Sensitivity to the prescribed AAD.
    - ii. Concurrent prescribed medications for other chronic diseases are contraindicated for the particular AAD prescribed.
6. When a subject complains to his/her Investigator about the medication and requests a cross-over to receive ablation, the Investigator will have little idea of the root cause of the subject's medication-related problem.

A cross-over management algorithmh could be used to help sort out disease progression issues from drug-related problems.

7. The following guidelines should be addressed by each investigator, prior to making a decision on a subject:

REASON TO INDUCE CROSS-OVER	REASON TO AVOID CROSS-OVER

 
1. Severe symptoms of AF in the absence of evidence that the subject was not taking the prescribed medication and consensus that further medication would be unsuccessful.
 
2. Severe side effects or AF symptoms, evidence of adherence to the prescribed AAD regimen, and no other drug options to which to switch the subject.
 
	
 
1. Evidence that the subject did not take the medications as prescribed and/or took concurrent incompatible medications for other chronic diseases – this subject should undergo Medication Managementi and then return to the hospital 3 weeks later for re-evaluation.
 
2. Evidence not sufficiently strong to merit cross-over, in the minds of the Investigator..
 

h A copy of this algorithm will be available to investigators in this trial as a reference guide to managing subjects with difficulties with their prescribed AAD.

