7. ANALYSIS POPULATIONS

The following analysis populations will be used to complete the analyses of data.

Cross-over subjects will be handled differently for each type of analysis population, as described subsequently. In general, subjects from the control group who have an ablation procedure after the primary endpoint is met will not be analyzed as cross-over.

Intent to treat (ITT) population: The ITT subject population will include all

subjects randomized, where subjects will be classified by the group to which they are randomized, regardless of the treatment received. For the ITT population, cross-over subjects will be included in the Control Group per randomization. Lost-to-follow-up and withdrawn/early termination subjects will also be included in the ITT population.

Per protocol (PP) population: The PP subject population will include randomized subjects who satisfy the following criteria, according to the treatment actually received:

- **Test Group:** subjects who
 - have undergone RF ablation,
 - are treated with the study catheter (THERMOCOOL[®] Catheter Family),
 - are in compliance (no major protocol deviations that has an impact on scientific value of the study) with the study protocol, and
 - have been treated for the study-related arrhythmia.
- **Control Group:** subjects who
 - have started an investigator-prescribed AAD and completed the dose-loading period (2 weeks),
 - have not undergone RF ablation,
 - are in compliance (no major protocol deviations that have an impact on scientific value of the study) with the study protocol, and
 - have been treated for the study-related arrhythmia.

All analyses conducted in the PP population will be as treated analyses. For descriptive tables and simple inferential models with fixed treatment effects subjects who have undergone RF ablation will be included in the Test Group regardless of the original treatment assigned (original randomization). Thus, cross-over subjects will be included in the Test Group for PP analyses. For more complicated inferential analyses, models will be applied where treatment itself is included as time-dependent covariate (see section 10.2 and 10.6.4). The approach described above applies for all tables which do not summarize data by visit (e.g. for time to event endpoints and other endpoints calculated overall per-patient). For summaries by visit and repeated measurement models, cross-over subjects will be completely excluded.

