Safety Population: The Safety Population will include all subjects who have undergone insertion of an ablation catheter, either as Test Group or cross-over subjects; and, subjects who started an investigator-prescribed AAD in the Control Group and did not initiate ablation therapy. Analysis of catheter-related complications will be limited to include only subjects who initiated ablation treatment (catheter insertion) either as Test Group and cross-over subjects.

Adverse drug reactions will be analyzed overall for all the subjects who have taken investigator-prescribed AAD and analyzed separately for cross-over subjects, those in the Test and Control Groups (excluding cross-over subjects).

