9. STUDY SUBJECTS AND DEMOGRAPHICS

9.1 Disposition of Subjects and Withdrawals

All subjects who provide informed consent will be accounted for in this study.

Disposition and study population summaries will be presented for all enrolled subjects by randomized treatment groups. Enrolled subjects are defined according to study protocol section 9.5 as subjects who sign the study informed consent form and are randomized. Thus, the set of enrolled subjects corresponds to the ITT population.

Descriptive summaries of population data will include the following:

- The number of subjects in each study population (ITT, PP, and Safety) will be summarized overall, by treatment group, and by study site.
- A listing sorted by randomized treatment group and subject will be provided that will include the reasons for exclusion from any of the study populations and the treatment assignment for the PP and Safety Population analyses.
- The number of subjects enrolled, excluded, discontinued, prematurely withdrawing from the study, lost to follow-up, died, not completed due to AE,

not completed due to other reasons, completed and the reasons for classification will be summarized.

- A listing of disposition as described above, including further details if available, will be provided for subjects in the ITT population.

A listing of screening failures (which are not randomized) with reason for screening failure will also be added.

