11.1 Adverse Events

An overall summary of AEs will be presented and will include the number and percentages of subjects with

- any adverse events
- catheter-related adverse events
- procedure related adverse events
- study drug related adverse events
- primary adverse events
- serious adverse events
- adverse events leading to withdrawal

All adverse events will be coded using MedDRA coding dictionary.

Summaries of incidence rates of individual AE (number and percentage of subjects) by MedDRA system organ class and preferred term will be prepared.

Such summaries will be displayed for all AE, AE by maximum severity and AE by strongest causality to catheter, procedure or study drugs.

In these summaries, each subject will be counted only once within each category. If a subject experiences more than one AE within a category, only the AE with the strongest causality or the maximum severity, as appropriate, will be included in the summaries by causality and severity.

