11.3 Serious AEs

The number and percentage of subjects with SAEs will be summarized by system organ class and preferred term for both treatment groups and overall and in a further table by causality and by severity.

The summary by AE category will also be prepared for serious catheter-related AEs and serious catheter-related AEs by timeframe. Three timeframes will be included in this summary: acute phase AEs (ablation to ≤ 7 days) and sub-chronic AEs (>7 to 30 days post ablation), and chronic AEs (occurring more than 30 days post ablation).

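### The general AE and SAE tables, grouped by treatment received, by implication count cross-over subjects' drug-period events under ablation and leave only never-ablated subjects in the drug column

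*SAP*

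**What the plan says.** Four parts of the SAP fix how safety events are grouped.

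- **Grouping rule (SAP 8.1).** "tables in the PP and Safety populations will summarize data by treatment actually received if not otherwise specified". Percentages use the number of subjects in the group as denominator, not person-time.
- **Who is on each side (SAP 7, Safety Population).** One limb takes "all subjects who have undergone insertion of an ablation catheter, either as Test Group or cross-over subjects". The other takes "subjects who started an investigator-prescribed AAD in the Control Group and did not initiate ablation therapy".
- **Unit of assignment (SAP 9.1).** A listing is to give each subject's population status and "the treatment assignment for the PP and Safety Population analyses". This is one label per subject, not one per event.
- **Table layout.** For serious events, SAP 11.3 says: "The number and percentage of subjects with SAEs will be summarized by system organ class and preferred term for both treatment groups and overall". For AEs in general, SAP 11.1 says: "Summaries of incidence rates of individual AE (number and percentage of subjects) by MedDRA system organ class and preferred term will be prepared". It names no columns and no split by onset before or after ablation.

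Elsewhere the SAP does separate cross-overs: in the catheter-related tables (11.2), the adverse drug reaction tables (11.5) and the baseline tables (9.3). Protocol 12.6.2 collects AEs from consent to the end of the study, so a cross-over subject's drug-period events are in the database. Protocol Appendix B lists among the reasons for cross-over: "Severe side effects or AF symptoms, evidence of adherence to the prescribed AAD regimen, and no other drug options".

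**The concern.** A subject who starts on drug, has a serious event, and is ablated a year later appears in the ablation column of a two-group table with that event. It is charged to a treatment not yet given. The same subject leaves the drug column, which is then selected on what happened after randomization. Appendix B itself warns that extensive cross-over could leave a younger, healthier and more compliant remainder on drug.

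The overall AE summary, the tables by system organ class and preferred term, and the SAE tables are where a reader will look for the overall safety contrast. No AE or SAE table by randomized group appears in SAP 11 or in the table list in 15.1, so no other summary table corrects the picture.

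**Working it through.** **Step 1: does the text lead there?** Under SAP 7, a cross-over subject cannot be in the drug limb of the Safety Population, because that limb requires that ablation was not initiated. The subject enters through catheter insertion. SAP 8.1 then groups by treatment received, SAP 9.1 gives one assignment per subject, and SAP 11.3 has two treatment groups. With two columns, only the ablation column is open to this subject. For SAP 11.1 the same follows by default, since no other layout is specified.

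**Step 2: how many subjects?** The plan states no figure for the safety comparison. The inputs are 161 per arm and 50% cross-over (Protocol 13.4, SAP 6). The effect size behind them checks: −ln(ln 0.95 / ln 0.85) = 1.153, against 1.154 stated. The sample size is not in dispute.

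- Cross-over subjects: 0.5 × 161 = 80.5
- Ablation column: 161 + 80.5 = 241.5, of which one third began on drug
- Drug column: 161 − 80.5 = 80.5

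**Step 3: treatments differ, cross-overs are typical (all rates assumed).** SAE hazard is 0.15 per year on drug and 0.10 after ablation, with 3 years of follow-up and cross-over time c uniform on 0 to b years.

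- Test: 1 − exp(−0.30) = 25.9%
- Drug column: 1 − exp(−0.45) = 36.2%
- Cross-over: average of 1 − exp(−[0.15c + 0.10(3 − c)]), which is 1 − exp(−0.30) × [1 − exp(−0.05b)] / (0.05b)

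| Mean cross-over time | Cross-over risk | Ablation column | Control as randomized |
|---|---|---|---|
| 0.75 y (b = 1.5) | 28.6% | (2 × 25.9 + 28.6)/3 = 26.8% | (36.2 + 28.6)/2 = 32.4% |
| 1.5 y (b = 3) | 31.2% | (2 × 25.9 + 31.2)/3 = 27.7% | (36.2 + 31.2)/2 = 33.7% |

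The ablation column exceeds the Test group by 0.9 to 1.8 points. The tabulated gap is 36.2 − 26.8 = 9.4 points, or 8.6 in the second row (unrounded). The randomized gap is 32.4 − 25.9 = 6.5 points, or 33.7 − 25.9 = 7.8. This example contains no selection of who stays on drug.

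**Step 4: treatments equal, cross-overs differ (assumed).** The 3-year SAE risk is 20% on either treatment, so h = −ln(0.8)/3 = 0.0744 per year. Cross-over is at 1 year, and the drug-period hazard of cross-overs is k times that of other Control subjects. Cross-over risk = 1 − exp(−[k·h + 2h]).

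| k | Cross-over risk | Tabulated: ablation vs drug | As randomized: Test vs Control |
|---|---|---|---|
| 0.5 | 17.0% | 19.0% vs 20.0% | 20.0% vs 18.5% |
| 1 | 20.0% | 20.0% vs 20.0% | 20.0% vs 20.0% |
| 2 | 25.7% | 21.9% vs 20.0% | 20.0% vs 22.9% |
| 3 | 31.1% | 23.7% vs 20.0% | 20.0% vs 25.5% |

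At k = 1, 2 and 3, about 6, 11 and 16 cross-over subjects with a drug-period event sit in the ablation column. With 25% or 10% cross-over and k = 2, the tabulated difference (ablation minus drug) is +1.1 or +0.5 points, against −1.4 or −0.6 as randomized (Test minus Control).

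**The case against.** Four points on the other side carry weight.

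- **The merge is inferred.** The only sentence that expressly puts cross-overs in the Test group is "Thus, cross-over subjects will be included in the Test Group for PP analyses", and it is limited to the PP population. SAP 7 says cross-overs are handled differently by population, and SAP 11.1 names no columns. A reader might infer that the SAP declares cross-overs to be ablation in every safety table; it does not. What stands is the implication of SAP 7, 8.1, 9.1 and 11.3 together. It is strong for the SAE tables and a default for the general AE tables.
- **The key safety endpoints are protected.** SAP 2.2.2 names catheter-related complications and adverse drug reactions, and both are shown with cross-overs apart. A severe side effect judged drug-related appears in the three-group tables of 11.5. SAP 11.1 and 11.3 also tabulate by causality, and SAE case listings are planned. What remains is chiefly events not judged drug- or catheter-related.
- **The tables are descriptive.** No formal safety test is planned. Cross-over for AF symptoms need not leave a misplaced event either, because AF recurrence alone is not an AE unless it worsens (Protocol 12.1.1).
- **The numbers are planning values.** SAP 5.1 records early termination, and the protocol aims to keep cross-over low. Smaller cross-over means smaller distortion.

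A reader might also take the reversed sign at k = 2 or 3 as a demonstrated bias against ablation. The documents supply no value of k, so it shows only what could happen.

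**Conclusion.** The concern holds within limits. As written, the SAP most naturally places cross-over subjects' pre-ablation AEs and SAEs under ablation and reduces the drug column to never-ablated Control subjects. It affects the two-group SAE tables and, by default, the general AE tables; the primary analysis and the two key safety endpoints are untouched.

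The 80 of 241 rests on the planned 161 per arm and 50% cross-over. The shift of 0.9 to 1.8 points in the ablation column rests on assumed SAE rates and on mean cross-over at 0.75 to 1.5 years. With equal hazards throughout, nothing is distorted. Whether the tables favour drug or ablation depends on how the cross-overs' drug-period risk compares with that of other Control subjects, which the documents do not say. This should be corrected before the safety tables are produced, but it does not threaten the trial's main conclusion.

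A related gap needs closing. SAP 7 says Control subjects ablated after the primary endpoint are not analysed as cross-over. They did initiate ablation, however, so they fit neither limb of the Safety Population. If they were kept in the drug column, their procedural events would be charged to drug.

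**What to change.** - In SAP 11.1 and 11.3, show three columns: Test, Control without cross-over, and cross-over. These are the subject groups SAP 11.5 already uses for adverse drug reactions.
- Within the cross-over column, split events by onset before or after first catheter insertion, and give patient-years for each period. This split is new; SAP 11.5 uses three exclusive subject groups and does not divide by date. Footnote that a cross-over subject can appear in both periods.
- Add one SAE table by randomized group.
- State in SAP 7 where Control subjects ablated after the primary endpoint are placed.

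The cost is programming, with more columns and smaller cell counts. No new data are needed: SAP 11.3 already requires serious catheter-related events to be timed relative to ablation (up to 7 days, more than 7 to 30, more than 30).

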8.2 Handling of Missing Data

There will be no imputation for the primary efficacy analysis and no sensitivity analysis with multiple imputation for the ITT population as the log rank test accounts for censored (independent of the reason) observations, which is sufficient also for subjects who could not be followed up for the planned period. Other data except treatment group assignment are not required for this testing method.

For the per protocol sensitivity analysis, the same applies to the time-to-event outcome (effectiveness endpoint) data.

For the derivation of the variable 'duration of AF', incomplete dates will be imputed with the mid point of the possible interval (15th of a month if only the day is missing, 1st of July if the month is missing as well). No further imputation is planned.

8.3 Derived Variables

Duration of AF [months]

Time between the recorded date of first AF and the date of randomization.

Time to persistent AF/AT

According to protocol, persistent AF/AT is defined as AF/AT lasting longer than 7 consecutive days or requiring termination by cardioversion after 48 hours. The primary endpoint is reached at the date of the first cardioversion after randomization (except cardioversion solely as part of a (re-)ablation procedure) or detection of persistent AF/AT by transtelephonic monitoring (TTM, performed between month 3 and month 36). The sponsor will review and adjudicate all events (progressions to persistent AF/AT), which were reported by the Investigator. Adjudication will already be performed for the interim analyses. All events where the sponsor confirmed in their final assessment that the primary endpoint was reached will be taken into account for analysis. The date at which the primary endpoint was reached will be taken as adjudicated by the sponsor or as reported by the Investigator (if no sponsor adjudicated date is available).

The protocol is not specific about the start date for time to event calculation. Originally according to SAP version 1.0 (which was applied for the interim analyses) time to event had been defined as the difference between randomization date and the date at which the endpoint was reached. However, after further discussion, it was decided to update the start date for time to event calculation for final analysis and to use date of procedure as start date for the test group, and date of randomization as start date for the control group.

This approach seems to be more appropriate and more conservative, as visit windows are calculated from date of procedure for test group. Otherwise, if time to event was calculated from date of randomization, test group would have longer follow-up period and longer time to each follow-up visit as control group.

If the primary endpoint is not observed during follow-up time, subjects will be regarded as censored at the completion visit/ last visit or at the last time TTM was recorded, whichever is later.

Time to persistent AF (HRS 2017)

According to the HRS consensus statement 2017, persistent AF is defined as continuous AF that is sustained beyond 7 days. The sponsor will provide an additional adjudication using this alternative definition of time to persistent AF. Based on this additional adjudication, a sensitivity analysis for time to persistent AF based on HRS 2017 will be performed.

AFEQT

Several summary scores will be derived from the responses to questions 1 to 20 of section 2 of the AFEQT questionnaire, for each of which responses between 1 (most desirable outcome) and 7 (least desirable outcome) can be given.

Using the following statistics, the scores are defined below:

- $S(a,b)$ is the sum of responses for the range of questions between a and b (both a and b included)
- $N(a,b)$ is the number of responses given for the range of questions between a and b (both a and b included)
- AFEQT Overall Score = $100 - (((S(1,18) - N(1,18)) * 100) / (N(1,18) * 6))$
- AFEQT Symptoms Subscale Score = $100 - (((S(1,4) - N(1,4)) * 100) / (N(1,4) * 6))$
- AFEQT Daily Activities Subscale Score =
= $100 - (((S(5,12) - N(5,12)) * 100) / (N(5,12) * 6))$
- AFEQT Treatment Concern Subscale Score =
= $100 - (((S(13,18) - N(13,18)) * 100) / (N(13,18) * 6))$
- AFEQT Treatment Satisfaction Subscale Score =
= $100 - (((S(19,20) - N(19,20)) * 100) / (N(19,20) * 6))$

EQ-5D

The EQ-5D questionnaire collects the EQ-5D visual analogue scale (VAS) score on a scale between 0 and 100 and five single items (mobility, self-care, activity, pain, and anxiety) with three response levels each (no problems, some problems, extreme problems). A summary score (EQ-5D health index) based on these five items will not be calculated, as this would require rather complex modelling using country-specific weights.

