### **11.4.3 Cardioversion for Arrhythmia Recurrence**

Unnecessary Cardioversion < 7 days should be discouraged, but within ethical bounds. If the investigator believes the subject's AF symptoms are sufficiently severe to warrant cardioversion, he/she should proceed, regardless of timing. AF symptoms sufficiently severe to warrant cardioversion are angina, shortness of breath and/or systolic blood pressure < 90 mmHg related to AF.

Subjects who undergo a cardioversion within 48 hours of arrhythmia recurrence are not considered as being progressed to persistent AF/AT, and, therefore, will not have reached the primary endpoint. These subjects will continue follow-up according to the protocol visit schedule through 3 years.

Subjects who undergo a cardioversion after 48 hours of arrhythmia recurrence are considered as being progressed to persistent AF/AT and, therefore, will have reached the primary endpoint. These subjects will continue to be followed continuously for safety and will be asked to return for a final assessment at the 3-year follow-up visit but not to participate in interim follow-up visits. All adverse events are to be reported by the investigator as per protocol requirements.

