2.2 Efficacy, Safety and Health Economic Endpoints

2.2.1 Efficacy Endpoints

The primary efficacy endpoint is the time to persistent AF/AT (excluding isthmus-dependent atrial flutter) at 3 years. According to the protocol, persistent AF/AT is defined as AF/AT lasting longer than 7 consecutive days or requiring termination by cardioversion after 48 hours.

Secondary efficacy endpoints are:

- Rate and time to persistent AF/AT at 1 year and 2 years, rate of persistent AF/AT by number of ablations at 3 years
- Number of repeat ablations and new anti-arrhythmic drugs (AAD) per subject throughout 3 years follow-up

- Rhythm (% subjects in sinus rhythm (SR), % subjects with recurrent AF/AT) throughout 3 years follow-up
- Factors associated with AF disease progression
 - Gender
 - Age
 - Left atrium (LA) size
 - HATCH score (score based on the five components: Hypertension, Age 75 years or older, Previous transient ischemic attack or stroke, Chronic obstructive pulmonary disease, and Heart failure)
 - Blood pressure
 - NYHA functional classification of heart disease
 - Presence of diabetes
 - Presence of hyperlipidemia or dyslipidemia
 - Presence of renal insufficiency
 - Presence of dementia

In addition, an alternative definition of the primary and the first secondary endpoint will be investigated based on the consensus statement of the HRS (Heart Rhythm Society, 2017). According to the HRS consensus statement 2017, persistent AF/AT is defined as continuous AF/AT that is sustained beyond 7 days.

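### The SAP 8.3 rule that dates the primary event at the first cardioversion omits the 48-hour condition in its own definition and in Protocol 11.4.3, and could count or misdate events if applied literally

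*SAP*

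**What the plan says.** **Definition.** SAP 2.2.1 and the opening of the time-to-event derivation in SAP 8.3 both carry the protocol definition: "persistent AF/AT is defined as AF/AT lasting longer than 7 consecutive days or requiring termination by cardioversion after 48 hours". Protocol 10.1 gives the same definition and names no recording method.

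**Operational rule.** The next sentence of SAP 8.3 says when the event occurs: "The primary endpoint is reached at the date of the first cardioversion after randomization (except cardioversion solely as part of a (re-)ablation procedure"). Its alternative route is detection of persistent AF/AT by TTM, which it describes as performed between months 3 and 36.

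**Protocol on cardioversion.** There are two adjacent exclusions. Protocol 11.4.3 says: "Subjects who undergo a cardioversion within 48 hours of arrhythmia recurrence are not considered as being progressed to persistent AF/AT", and keeps these subjects on the visit schedule. It adds the converse: "Subjects who undergo a cardioversion after 48 hours of arrhythmia recurrence are considered as being progressed to persistent AF/AT". Protocol 11.4.4 excludes cardioversion done solely within an ablation or re-ablation.

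**Adjudication.** SAP 8.3 continues: "The sponsor will review and adjudicate all events (progressions to persistent AF/AT), which were reported by the Investigator". Then: "All events where the sponsor confirmed in their final assessment that the primary endpoint was reached will be taken into account for analysis". The event date "will be taken as adjudicated by the sponsor or as reported by the Investigator (if no sponsor adjudicated date is available").

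**The concern.** SAP 8.3 contradicts itself in consecutive sentences. The definition needs AF/AT to have lasted more than 48 hours before a cardioversion counts. The dating rule needs only a first cardioversion. The rule reproduces one of the protocol's two exclusions (11.4.4) and leaves out its neighbour (11.4.3), and a single stated exception invites the reading that there are no others.

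The omitted case can occur. Protocol 11.4.3 discourages early cardioversion but allows it for severe symptoms at any time. Subjects cardioverted within 48 hours stay in follow-up, so one subject can have an early non-endpoint cardioversion and a true progression later. The word "first" then selects the wrong date.

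Two errors are possible under a literal reading:
- a subject who never progressed is counted as an event;
- a subject who did progress is dated too early.

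The route for AF/AT beyond 7 days is also narrower than the protocol's. Naming TTM alone leaves unclear how an episode documented by ECG or Holter, or before TTM starts (Day 104 in Protocol 11.2.1), is to be dated.

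This is the derivation of the primary endpoint in a trial planned on few events (28 at the last look of the SAP 10.4 example table), so a small number of wrong events or dates matters.

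**Working it through.** **Step 1. Set the rules side by side.**

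| Case | Protocol | SAP definition (2.2.1, 8.3) | SAP 8.3 dating rule, read literally |
|---|---|---|---|
| Cardioversion within 48 h | Not an event (11.4.3) | Not an event | Event |
| Cardioversion after 48 h | Event (11.4.3) | Event | Event |
| Cardioversion solely within (re-)ablation | Not an event (11.4.4) | Not addressed | Not an event |
| Within 48 h first, true event later | Event at the later date | Event at the later date | Event at the earlier date |
| AF/AT beyond 7 days, not cardioverted, not on TTM | Event (10.1) | Event | Not named |

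The dating rule departs from the protocol in the first and fourth rows and is silent in the fifth.

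**Step 2. Reproduce the plan's figure.** Inputs from SAP 6: three-year event-free proportions 0.85 (control, after cross-over) and 0.95 (test), 10% drop-out over 3 years, 1.5 years' accrual, 161 per arm, one-sided alpha 0.025, 85% power. The final bound 2.0507 is from the SAP 10.4 example table.

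- Hazards per year: control −ln(0.85)/3 = 0.0542; test −ln(0.95)/3 = 0.0171; drop-out η = −ln(0.90)/3 = 0.0351.
- HR = ln(0.95)/ln(0.85) = 0.0513/0.1625 = 0.316.
- A pooled two-proportion formula for 15% against 5% gives 161 per arm, the plan's 322, without drop-out inflation.
- Exponential model with follow-up to a common end at 4.5 years. The event probability per arm is p = λ/(λ+η) × [1 − e^(−(λ+η)f)], averaged over f from 3 to 4.5 years. This gives p = 0.172 (control) and 0.058 (test), or 27.7 and 9.4 events.
- SE of ln HR = √(1/27.7 + 1/9.4) = 0.378. Power = Φ(1.153/0.378 − 2.0507) = Φ(1.00) = 84%. The N required for 85% is 330, within 2.5% of 322.

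This model expects about 37 events, against 28 in the SAP table, so the powers below are approximate.

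**Step 3. Add wrongly counted cardioversions.** The documents give no rate of cardioversion within 48 hours. Let q be an assumed three-year rate of such cardioversions that are wrongly accepted as events. With q equal in both arms:

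HR(q) = ln[0.95(1−q)] / ln[0.85(1−q)]

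| q per arm | HR | Events (control, test) | SE | Power at 2.0507 |
|---|---|---|---|---|
| 0 | 0.316 | 27.7, 9.4 | 0.378 | 84% |
| 1% | 0.0613/0.1726 = 0.36 | 29.3, 11.1 | 0.352 | 81% |
| 2% | 0.0715/0.1827 = 0.39 | 30.8, 12.9 | 0.332 | 78% |
| 5% | 0.1026/0.2138 = 0.48 | 35.4, 18.2 | 0.289 | 69% |
| 10% | 0.1567/0.2679 = 0.58 | 43.0, 26.8 | 0.246 | 55% |

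**Step 4. Put them in one arm only (5%).**

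- Control only: HR = ln(0.95)/ln(0.8075) = 0.0513/0.2138 = 0.24.
- Test only: HR = ln(0.9025)/ln(0.85) = 0.1026/0.1625 = 0.63.

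The direction therefore depends on where the early cardioversions fall.

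**Step 5. Effect of a single event.** With d events and equal allocation, Z ≈ (d/2 − test events)/√(d/4). Take an illustrative split of the 28 events.

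- 8 v 20 (test v control): Z = 6/√7 = 2.27.
- One false test event, 9 v 20: Z = 5.5/√7.25 = 2.04, just under 2.0507.
- One false control event, 8 v 21: Z = 6.5/√7.25 = 2.41.

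This shows sensitivity near the bound. It does not forecast the trial's result. Misdating changes the order of events and not their number, and is not quantified here.

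**The case against.** The strongest reply is that the dating sentence does not decide what enters the analysis. The 48-hour condition stands in SAP 2.2.1 and immediately before the sentence, which can be read as dating an event already defined. Investigators report progressions under Protocol 11.4.3, the sponsor confirms them, and the confirmed date is used. Nothing says that a programmer derives events from raw cardioversion records, or that the adjudicator works from the faulty sentence. Cardioversions and adjudication forms are listed (Listings 16.2.31 and 16.2.17.2). The HRS 2017 sensitivity analysis has its own adjudication and uses only AF sustained beyond 7 days, so the cardioversion route does not touch it.

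Much of this stands, and it rules out several stronger readings:

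- A reader might infer that the SAP abandons the 48-hour condition, or that early cardioversions will be counted. Neither follows, because the definition and the adjudication step remain.
- A reader might infer that AF/AT beyond 7 days seen on ECG or Holter can never be an event. The adjudication sentence covers all investigator-reported progressions without limit by recording type.
- A reader might expect dilution towards no effect. That needs similar rates in both arms, as Step 4 shows.
- A reader might infer that one or two events will decide the trial. The 28 events and the 2.0507 bound belong to a table that SAP 10.4 presents as an example, and SAP 5.1 says the study ended early and spends the remaining alpha.

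The reply does not remove the contradiction. SAP 8.3 prints no adjudication criteria beyond two sentences that disagree. The sponsor adjudicates in an open-label trial, and Protocol 15.5 leaves an endpoint committee optional. Where there is no adjudicated date, the investigator's is used.

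**Conclusion.** The sentence is wrong as written. It omits the 48-hour condition, carries over only one of the protocol's two cardioversion exclusions, and conflicts with the definition just before it. Programmed or adjudicated literally, it could count cardioversions that are not endpoints or date a true event too early. Naming only TTM for the 7-day limb is a second, lesser mismatch with Protocol 10.1.

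How much this matters is not known from the documents. The figures in Steps 3 and 4 assume constant hazards, the planning rates, an invented rate of early cardioversion, and an adjudication process that lets every such case through. If adjudication follows Protocol 11.4.3, the effect is nil. The sample size, power and planning hazard ratio are unaffected, because the planning rates are for disease progression. The point should still be settled before the final analysis, because it concerns the stated rule for the primary endpoint.

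**What to change.** Reconcile the SAP 8.3 sentence with Protocol 10.1, 11.4.3 and 11.4.4. Suggested content: the event date is the earlier of

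- the first cardioversion performed after 48 hours of AF/AT, other than one solely part of an ablation or re-ablation procedure; and
- detection of AF/AT lasting longer than 7 consecutive days, by TTM or another documented recording.

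State that cardioversions within 48 hours are listed but neither counted nor used to date an event. Put the same wording on the adjudication form. Before lock, compare the adjudicated dates, and any investigator dates used as fallback, with the cardioversion listing.

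The cost is one SAP sentence, matching text on the form, and a review of a small number of events.
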